4.2 Patient Identification and Consent

All patients with an appointment for a renal mass at UNC Chapel Hill Hospital may

be approached in person for consent. In a private clinic room, study staff will review consent documents with potential participants and answer any questions. If a patient desires additional time or wishes to delay enrollment in the study, he/she will be given a copy of the consent document and informed about how to ask questions or enroll at a later date. Enrollment and informed consent will be facilitated by the study coordinator. If the subject chooses to participate in the study, he or she signs the consent and is given a copy for his/her own records.

If at any point in this process the patient declines, fails to meet eligibility criteria, or is otherwise unable to fulfill the requirements of the research, he or she is excluded from further participation. Patients will be provided assurance that declining participation will not affect their clinical care.

4.3 Blood Draw for Creatinine

If subjects do not have a serum creatinine value within 30 days prior to a scheduled PET-MRI scan, they will be required to have a blood draw at UNC Hospitals for creatinine before their PET-MRI scan visit. This is the normal procedure prior to nephrectomy, and so these blood values can also be used for PET-MRI scans. . Serum creatinine must be less than 1.8mg/dL in order to proceed with the Dynamic Contrast Enhancement MRI part of the scan. If the subject does not meet that level, the subject will be imaged with the other non-contrast sequences and with PET since the non-contrast images will still meet the primary objective of the study.

4.4 FDG-PET-MRI

All patients will undergo a MRI scan with simultaneous acquisition of [¹⁸F] Fludeoxyglucose Positron Emission Tomography (FDG F18- PET). 18F-FDG is a positron-emitting radiopharmaceutical used for diagnostic purposes. It is a glucose analog that concentrates in cells relying upon glucose as an energy source or in cells whose reliance on glucose increases under pathophysiological conditions. Each participant will receive approximately 12 mCi 18F-FDG, the exact dose administered to each participant will be measured and recorded in the study records

Subjects will have a finger-stick blood glucose test upon reporting to the imaging center; blood glucose must be below 200 mg/dL in order to proceed with the FDG injection. If blood glucose exceeds this level, a second finger-stick test may be performed after 30 minutes, and if the second test is below the threshold, the FDG injection may proceed. Failing the second test will result in the subject being rescheduled for another day or excluded from the study.

Injection of gadolinium contrast agent (if the serum creatinine test is passed: serum creatinine < 1.8 mg/dL) will be performed in the usual manner and images simultaneously obtained with MRI. If the serum creatinine is above the threshold, the subject will not receive gadolinium contrast, but the remainder of the scanning protocol will proceed.

Patients will have fasted for at least 6 hours before intravenous injection of FDG. To minimize radiation-absorbed dose to the bladder, patients should drink at least an 8 ounce glass of water prior to drug administration. Whenever possible, patients should take the following precautions for 12 hours after injection: used toilets should be flushed several times after each use, and hands should be washed thoroughly. If blood, urine or feces soil clothing, the clothing should be washed separately.

Each patient will be imaged at a single visit. Patients will be scheduled for PET-MRI imaging at Marsico Hall and will receive imaging-day instructions from the study coordinator. The study coordinator will meet the patient at the imaging facility and escort them to the imaging suite. Women of childbearing potential will undergo urine pregnancy test the day of and prior to the PET/MRI.

Patients will be paid \$50 each upon completion of the imaging visit as compensation for their time.

4.5 Duration of Study Intervention

The study intervention is complete once the patient receives their PET-MRI scan. The patient may be withdrawn from the study prior to this point if any of the following apply:

- Inter-current illness prevents completion of imaging studies
- Unacceptable adverse event(s) prevents completion of imaging studies
- Patient decides to withdraw from the study, **OR**
- General or specific changes in the patient's condition render the patient unacceptable for completion of study in the judgment of the investigator.

After PET-MRI, patients will undergo nephrectomy as planned and per standard of care and tumors will be sampled as above (up to 10 cores will be taken from each tumor post-surgery and classified as ccA or ccB subtype using transcriptome analysis).

4.6 Duration of Follow Up

Patients will be followed up via review of their medical records through disease recurrence or survival for up to 5 years.

4.7 Removal of Patients from Protocol

Patients may be removed if they experience unanticipated claustrophobia causing intolerance to the MR. If patients require lorazepam in order to tolerate the MR, they will be withdrawn from study participation.

4.8 Abstraction of Medical Records

Medical records will be reviewed and data extracted for clinical outcomes. Pathologic stage, as well as any information on recurrence and survival.

Information collected may help to establish preliminary data for future studies.

5.0 TIME AND EVENTS TABLE

	Pre-Study	Imaging	Surgery	Long-term follow-up ¹
Screening	X			
Informed Consent	X			
Pregnancy test²		X		
Creatinine blood draw	X ³			
PET-MRI		X		
Glucose Test		X		
Surgery			X	
Collection of Surgical Tissue			X	
Abstraction of Medical Records				X

¹Long-term follow-up will be restricted to abstraction of medical records for any data on recurrence and/or survival for up to five years post treatment.

²If clinically applicable women of childbearing potential will undergo urine pregnancy test the day of and prior to PET-MRI imaging

³Creatinine should be drawn within 30 days of PET-MRI imaging

6.0 EXPECTED RISKS/UNANTICIPATED PROBLEMS

6.1 Assessment of Safety

In general, any patient enrolled on this protocol and who undergoes any portion of the PET-MRI study (including gadolinium administration) will be evaluable for adverse events.

6.2 Expected Risks

6.2.1 Risks of PET/MRI

Emotional Distress

Emotional distress is possible during MRI. Technologists will ask subjects, before injection, if they are claustrophobic. Also, technologists will do their best to help comfort any subject who is claustrophobic but chooses to continue. Technologists will hand subjects a squeeze ball alarm and instruct them to use it in case of any discomfort. The technologist will also inform the subject that she is free to stop at any time, for any reason.

Radiation

Radiation: The PET/MRI scans will expose study participants to controlled amounts of limited radiation. The total dose of radiation from these tests is not anticipated to cause any adverse effects of any significance over that which they may experience over their standard of care diagnostic imaging and subsequent therapies. Patients enrolled in this pilot study will receive an estimated dose of radiation as specified by the Radiation Safety Committee. The amount of risk to this estimated dose will be equated to the annual radiation exposure limit for radiation workers in the informed consent. This radiation exposure involves a small risk and is necessary to obtain the information desired.

This research study involves exposure to radiation from radiotracer (approximately 12 milliCuries 18F-FDG) used for PET/MR scan. The radiation dose subjects will receive in this study is 1.3 rem. For comparison, a person in the United States receives a radiation exposure of 0.3 rem per year from natural background sources. The radiation dose that subjects will receive in this study is equivalent to the radiation exposure that everyone receives in 4.3 years from natural background radiation for participants completing the PET scan. For comparison, the people who work with radiation (radiation workers) are allowed to receive a radiation dose of 5 rem per year. The amount of radiation exposure received in this study is equal to 26 % of the annual radiation exposure limit for radiation workers. This radiation exposure involves only a small risk and is necessary to obtain the research information desired. The radiation exposure described here is what subjects will get from this research study only. It does not include any exposure subjects may have received or will receive from other tests outside of this study that are a part of their medical care.

FDG

Information about FDG F18 was obtained from the Prescribing Information (August 5 2004); <http://www.accessdata.fda.gov/scripts/cder/drugsatfda/>. According to this document , reviews of the oncology literature did not reveal reported adverse reactions when using 18F-FDG as a diagnostic in conjunction with PET. In a subset (n=42) of a safety database of epilepsy patients (n=374), 4 patients had transient hypotension, 6 had hypo- or hyperglycemia and 3 had transient increases in alkaline phosphatase.

Gadolinium

An extremely rare disease called Nephrogenic Systemic Fibrosis (NSF) is associated with the use of gadolinium contrast agents in patients with chronic severe renal insufficiency or renal dysfunction due to hepato-renal syndrome or in the peri-operative liver transplantation period. Exclusion criteria for this study are in compliance with the Food and Drug Administration's advisory statements.

As part of the MRI procedure subjects may receive a dye called gadolinium. Gadolinium makes it easier to see details on the MRI pictures. If subjects have any problems with their kidneys, they may be at risk for a condition called Nephrogenic

Systemic Fibrosis (NSF) or Nephrogenic Fibrosing Dermopathy. NSF has been reported to occur between 2 days and 18 months following injection of gadolinium. There is no known treatment for NSF. Some people have even died from this. Signs and symptoms of NSF may include: burning, swelling, hardening or tightening of the skin, blood vessels and internal organs (heart, lungs, liver; yellow spots on the white part of the eyes; joint swelling and stiffness; pain in the hip bones or ribs; muscle weakness.

Subjects' study doctor will check how well their kidneys work before they are given gadolinium. Depending on how well their kidneys work, they may not be given gadolinium at all. NSF has not been reported in people with normal kidneys.

Small amounts of gadolinium can stay in the body including the brain, bones, skin and other parts of the body for a long time (several months to years) in people with normal kidney function. People who get many doses of gadolinium medicines, women who are pregnant and young children may be at increased risk from gadolinium staying in the body. So far, studies have not found harmful effects of gadolinium in patients with normal kidneys. Rarely, patients have reported pains, tiredness, and skin, muscle or bone ailments for a long time, but these symptoms have not been directly linked to gadolinium.

6.3 Unanticipated Problems

6.3.1 Definition

As defined by UNC's IRB, unanticipated problems involving risks to study subjects refers to any incident, experience, or outcome that:

- Is unexpected (in terms of nature, severity, or frequency) given (a) the research procedures that are described in the protocol-related documents, such as the IRB-approved research protocol and informed consent document; and (b) the characteristics of the subject population being studied;
- Is related or possibly related to a subject's participation in the research; and
- Suggests that the research places subjects or others at a greater risk of harm (including physical, psychological, economic, or social harm) related to the research than was previously known or recognized.

6.3.2 Reporting

Any unanticipated problem that occurs during the conduct of this study and that meets **at least** the first two criteria listed in 6.3.1 must be reported to the UNC IRB using the IRB's web-based reporting system.

6.4 Data and Safety Monitoring Plan

The Principal Investigator will provide continuous monitoring of patient safety in this trial with periodic reporting to the Data and Safety Monitoring Committee (DSMC).

Meetings/teleconferences will be held at a frequency dependent on study accrual, and in consultation with the study Biostatistician. These meetings will include the investigators as well as protocol nurses, clinical research associates, regulatory associates, data managers, biostatisticians, and any other relevant personnel the principal investigators may deem appropriate. At these meetings, the research team will discuss all issues relevant to study progress, including enrollment, safety, regulatory, data collection, etc.

The team will produce summaries or minutes of these meetings. These summaries will be available for inspection when requested by any of the regulatory bodies charged with the safety of human subjects and the integrity of data including, but not limited to, the oversight (Office of Human Research Ethics (OHRE) Biomedical IRB, the Oncology Protocol Review Committee (PRC) or the North Carolina TraCS Institute Data and Safety Monitoring Board (DSMB).

The UNC LCCC Data and Safety Monitoring Committee (DSMC) will review the study on a regular (quarterly to annually) basis, with the frequency of review based on risk and complexity as determined by the UNC Protocol Review Committee. The UNC PI will be responsible for submitting the following information for review: 1) safety and accrual data including the number of patients treated; 2) significant developments reported in the literature that may affect the safety of participants or the ethics of the study; 3) preliminary response data; and 4) summaries of team meetings that have occurred since the last report. Findings of the DSMC review will be disseminated by memo to the UNC PI, PRC, and the UNC IRB and DSMB.

7.0 STATISTICAL CONSIDERATIONS

7.1 Study Design/Study Endpoints

The purpose of the study is to assess the utility of combined, simultaneous positron emission tomography (PET) and magnetic resonance imaging (MRI), collectively called PET-MR, in predicting the fraction of tumor cores expressing the ccB subtype. The overall design is to image patients with PET-MR prior to surgery and evaluate quantitative metrics from imaging, and to evaluate the correlation of imaging metrics with the results of post-surgery transcriptome analysis. The primary endpoint is to correlate the MRI-guided PET metric fractional tumor volume over threshold SUV > 2.0 (FTVOT2) with the fraction of tumor cores classified as ccB from transcriptome analysis.

Patients will have suspected ccRCC based on imaging with tumor size ≥ 4 cm and for whom surgical treatment is planned. Once patient identification occurs, the patient will be assessed for the study via the inclusion and exclusion criteria mentioned above. The patient will then be approached by a study coordinator and

the study protocol explained and all risks outlined. If the patient provides informed consent the patient will be enrolled. Demographic data such as patient age, gender, comorbidities, and previous treatments, etc. will be collected. Tumor characteristics will be collected. All data collected will be kept on a password protected, secured server, and all physical documentation will be stored in a locked cabinet. All data will be collected by the PI, co-investigators and study coordinators.

Patients will then be scheduled for a pre-surgery PET-MR within four weeks of planned surgery.

For all PET scans, patients will be instructed to fast, and blood glucose level will be measured prior to injection of FDG; if blood glucose exceeds 200 mg/dL after two finger-stick tests, the patient will be rescheduled for another day or excluded from the study. Patients will be injected with approximately 12 mCi 18F-FDG, and then imaged starting 60 minutes post-injection for ten minutes each at one or two bed positions focused on the primary tumor site. MRI sequences to be run will include conventional anatomic T1- and T2-weighted sequences, high-resolution T1 pre- and post-contrast DCE sequences, and the PET-MR attenuation-correction sequence.

The PET-MRs will be evaluated retrospectively by study personnel as to the size of the lesion, the FDG activity as measured by tumor-maximum and tumor-mean standard uptake values (SUVs), additional PET metrics (metabolic tumor volume (MTV) and total lesion glycolysis (TLG)), the presence or absence of invasion to adjacent organs, and the presence or absence of metastatic or multifocal disease. PET images will be evaluated with aligned anatomical MRI for guidance as well as determination of the tumor margins for computation of tumor-mean SUV, and FTVOT2.

The pathological specimens will be evaluated by a UNC pathologist. Again, all data will be stored on a secured, password protected server. Up to ten samples will be taken from each tumor, spatially distributed, and stored according to lab manual. Non-ccRCC histologies will be excluded from further analysis. RNA will be extracted and each sample will be classified as ccA or ccB using the ClearCode34 Nanostring classifier as previously described using a 34-gene custom Nanostring probe (NanoString Technologies, Seattle, WA).[13] Each sample will then be categorized as ccB or ccA or equivocal. If both tumor types appear in the same sample, the classifier will choose the closest match; however, each result will be reviewed and samples that show clear elements of both types in expression patterns will be labeled as equivocal. The fraction of samples classified as clearly ccB will be used in further analysis.

To address the primary endpoint, FTVOT2 will be evaluated and recorded for each subject as will the fraction of samples classified as ccB.

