1.0 BACKGROUND AND RATIONALE

1.1 Study Synopsis

The objective of this study is to evaluate the utility of simultaneous positron emission tomography (PET) and magnetic resonance imaging (MRI) in characterizing the molecular subtypes of clear cell renal cell carcinomas (ccRCC) to potentially inform prognosis and treatment decisions. Previous results on a small number of subjects at UNC demonstrated a relationship between PET-MRI imaging characteristics and tumor subtype composition as determined by transcriptome analysis of surgical core samples in ccRCC. ccRCC has been classified into two molecular subtypes, ccA and ccB, on the basis of expression of a group of 34 genes; the two subtypes have been shown to have clear differences in prognosis. These tumors are notoriously heterogeneous; a single tumor can contain both subtypes, and full tumor molecular characterization is infeasible. Imaging, however, offers a snapshot of the whole tumor. If imaging characteristics prove to be predictive of subtype composition, early prognostic information would be available and different approaches to treatment may be enabled.

In this project, we will image 17 ccRCC subjects on simultaneous PET-MRI and quantify the metabolically-active fraction of the tumor from images. Up to ten core samples will be taken from each tumor post-surgery and classified as ccA or ccB subtype using transcriptome analysis. The imaging-based measures will be correlated with the fraction of tumor cores classified as ccB. We hypothesize that the metabolically-active tumor volume fraction derived from simultaneous PET-MRI imaging is correlated with the fraction of tumor cores classified as ccB subtype from transcriptome analysis.

This study is designed to provide preliminary information on the relationship between imaging metrics and tumor subtype composition in 17 ccRCC subjects. The primary objective is to evaluate the capabilities of MRI/PET in prediction of ccB burden.

Information from this study may be used to estimate effect size for power calculation and sample size considerations for possible future studies in the use of combined PET-MR to be used for prognostic information in ccRCC cases and potentially to enable risk-stratification that is not currently possible.

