Patients will undergo nephrectomy within 4 weeks of imaging. Up to ten samples will be taken from each tumor, spatially distributed, and stored according the lab manual. Non-ccRCC histologies will be excluded from further analysis. RNA will be extracted and each sample will be classified as ccA or ccB using the ClearCode34 Nanostring classifier as previously described using a 34-gene custom Nanostring probe (NanoString Technologies, Seattle, WA).[13] Each sample will then be categorized as ccB or ccA or equivocal. The fraction of samples classified as ccB will be used in further analysis.

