7.3 Data Analysis Plans

For the primary endpoint, each subject's FTVOT2 will be correlated with the primary outcome (fraction of core classified as ccB) and correlation estimated using the non-parametric Spearman correlation test.

Regarding the specific hypothesis testing of PET FTVOT2, with $N = 17$, we will have approximately 54% power to detect a correlation of $\rho = 0.5$ (and 74% power to detect $\rho = 0.6$), with a Type I error rate of 0.05 and utilizing the Spearman correlation test. This is considered a conservative estimate. Data from the prior study¹ shows a strong Spearman correlation ($\rho = .896$, $p = .006$) between the fraction of core samples classified as ccB and the PET tumor volume fraction over SUV 2.0 (FTVOT2).

¹ S. A. Brooks et al., "Alternate metabolic programs define regional variation of relevant biological features in renal cell carcinoma progression," *Clinical Cancer Research*, Jan 19, 2016. (PMID: 26787754)

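### Is the primary outcome left undefined because no rule says whether equivocal cores count in the denominator of the ccB fraction?

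*Combined protocol and SAP*

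**What the plan says.** Section 7.1 describes two steps. The classifier first assigns each core to its nearest subtype. Every result is then reviewed, and "samples that show clear elements of both types in expression patterns will be labeled as equivocal". The outcome follows: "The fraction of samples classified as clearly ccB will be used in further analysis". Section 1.3 has the same three labels: "Each sample will then be categorized as ccB or ccA or equivocal".

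Three other places are shorter. Section 1.1 says "Up to ten core samples will be taken from each tumor post-surgery and classified as ccA or ccB subtype using transcriptome analysis" and then "The imaging-based measures will be correlated with the fraction of tumor cores classified as ccB". Section 4.5 says "up to 10 cores will be taken from each tumor post-surgery and classified as ccA or ccB subtype using transcriptome analysis". Section 7.3 names "the primary outcome (fraction of core classified as ccB" as the variable to be correlated with FTVOT2, without the qualifier about clear calls, "with a Type I error rate of 0.05 and utilizing the Spearman correlation test". Section 7.2 sets enrollment at 17 patients. No section gives an expected share of equivocal cores.

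**The concern.** A fraction needs a numerator and a denominator, and the plan words only the first explicitly. If equivocal cores stay in the denominator, a mixed core counts the same as a ccA core. If they are dropped, a tumor with five ccB and five equivocal cores scores 1.0, and one with only equivocal cores has no score. Read alone, sections 1.1 and 4.5 even suggest a third scoring, in which every core keeps the classifier's closest match.

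Spearman's test uses only ranks, and with 17 patients a few changed ranks can move a p-value across 0.05. If the scoring were chosen after the core results had been set against FTVOT2, the stated Type I error rate would no longer hold.

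**Working it through.** **The plan's own power figures.** Section 7.3 states 54% power at ρ = 0.5 and 74% at ρ = 0.6, with N = 17 and alpha 0.05. The Fisher z approximation is power = Φ(atanh(ρ)·√(n−3) − 1.96), two-sided, with √14 = 3.742.

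- ρ = 0.5: 0.5493 × 3.742 − 1.96 = 0.095; Φ = 53.8%.
- ρ = 0.6: 0.6931 × 3.742 − 1.96 = 0.634; Φ = 73.7%.

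Both reproduce. Core scoring does not enter the formula, so the question does not touch these figures.

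**How many scorings the text allows.**

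- *Closest match for every core.* Section 7.1 gives the closest-match call as its first step and then overrides it for mixed cores on review. Counting only clear ccB calls rules this scoring out. Section 1.1 is a synopsis. The wording in section 4.5 is a parenthesis in a section about duration, and it refers back to the sampling already described.
- *Equivocal cores dropped.* No sentence says so. The same paragraph of section 7.1 expressly removes tissue that is not ccRCC, so its authors state exclusions when they intend them.
- *Equivocal cores kept.* This is the literal reading, because the fraction is taken of the samples.

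At most two scorings are therefore open, and the text favors keeping.

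**What the choice does to ranks.** These are illustrative counts with 10 cores per tumor. Tumor A has 5 ccB, 2 equivocal and 3 ccA. Tumor B has 6 ccB and 4 ccA.

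| Scoring | A | B | Order |
|---|---|---|---|
| Kept | 5/10 = 0.50 | 6/10 = 0.60 | A below B |
| Dropped | 5/8 = 0.625 | 6/10 = 0.60 | A above B |

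A tumor with 10 equivocal cores scores 0/10 = 0 if they are kept, and 0/0 if they are dropped.

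**Size by simulation.** N = 17 is from section 7.2, and 10 cores is the maximum in section 7.1. Assumed: tumor ccB proportion Beta(0.7, 1.2), equivocal share 10%, 20% or 30%, and several models of how equivocal calls arise. The test is the two-sided Spearman t-test, t = r·√(15/(1 − r²)) on 15 degrees of freedom. Verdict differences are at a true rank correlation of 0.6; false positives are at zero correlation.

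| Equivocal share (assumed) | Verdict differs, kept v dropped | False positives, better of the two |
|---|---|---|
| 10% | 5–7% | 6.0–6.1% |
| 20% | 6–11% | 6.0–6.5% |
| 30% | 7–16% | 6.5–7.2% |

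Each scoring fixed in advance gives 5.0% to 5.4% false positives. At 30% equivocal, power for kept against dropped runs from 62% v 59% in one model to 49% v 55% in another, so neither is reliably better. Dropping leaves at least one patient without an outcome in 0% to 14% of trials at that rate. With no equivocal cores, all differences are zero.

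**The case for a change.** The strongest case for a change is that this is the primary outcome, that the protocol itself expects mixed cores, and that one sentence would settle the matter. Section 1.1 stresses heterogeneity, and section 7.1 has every result reviewed for mixture. The study is preliminary, but section 7.3 still states a hypothesis test, and section 1.1 foresees using the results to plan later studies. Counting the closest-match call as a third scoring would raise the verdict differences to 9–26% and the best-of-three false positives to 6.5–8.6%.

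Part of this stands. The denominator is not written as a rule, section 7.3 omits the qualifier, and a verdict difference of up to 16% in a 17-patient study is not trivial if equivocal cores are common. The three-way figures do not stand, because they rely on a scoring that section 7.1 excludes. The false-positive figures describe an analyst who computes both fractions and reports the more favorable; they do not describe one who follows section 7.1. A sentence making the rule explicit would adopt the reading the text already favors, so it would change neither the outcome nor the test. Re-scoring with equivocal cores excluded is a reasonable optional check, but it is not a better primary method.

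**Conclusion.** No change to the plan follows. This is a gap in wording that an analyst reading section 7.1 would fill sensibly: clearly ccB cores divided by all classified cores, with equivocal cores kept. That outcome exists for every patient with at least one classified core, and as a fixed rule it holds the Type I error at about 5%. The shorter wording in sections 1.1, 4.5 and 7.3 is abbreviation.

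The residual exposure is the choice between keeping and dropping: a different p<0.05 verdict in about 5–16% of trials, and false positives of about 6–7% if the better result were selected. Both ranges rest on assumed equivocal shares of 10–30%, an assumed Beta shape and a full 10 cores per tumor. No direction of bias and no consistent gain in power is shown for either scoring. A clarifying sentence at the next convenient amendment would be harmless, but the analysis is sound without it.

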Nonmetastatic clear cell renal cell carcinomas are generally treated with nephrectomy, although research has subclassified them into two [8] or as many as four [9] subtypes based on gene expression; the subtypes have been shown to have differing prognoses and progression [8]–[11]. We focus primarily on the two subtypes ccA and ccB [8] and ask whether these two exhibit distinct PET-MRI imaging characteristics that can be used to subtype them noninvasively. An eight-subject pilot study conducted on PET-MRI at UNC demonstrated that quantitative PET-MRI imaging, using nonstandard measures incorporating the entire tumor, was strongly correlated with presence or absence of ccB patterns in the tumors [12]. Transcriptome analysis results from the study justified the import of PET in noting that many of the upregulated genes associated with ccB were involved in glucose transport and metabolism, the mediators of 18-FDG uptake. Thus, there is a strong biologic rationale as to why PET-MRI could predict ccB burden, but the small number of subjects in that study limits confidence. Also, the fact that these tumors are highly heterogeneous suggests that imaging alone provides an opportunity for early characterization of ccB burden across the entire tumor where gene expression profiling would be invasive and costly. Also, with the excellent soft-tissue contrast of MRI, the system has the potential for greater anatomical detail to guide interpretation of FDG activity. UNC has one of the few PET-MR scanners in the country, making it one of few centers in the US capable of conducting this study.

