2.0 STUDY OBJECTIVES/AIMS AND ENDPOINTS

2.1 Primary objectives

- 2.1.1** To correlate quantitative metrics from imaging characterizing the tumor volume fraction associated with medium-to-high 18-FDG-PET uptake with the fraction of ccB-positive cores based on transcript analysis

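### Should a core with mixed ccA and ccB expression earn part credit in the primary outcome?

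*Combined protocol and SAP*

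**What the plan says.** Section 7.1 allows three labels per core: ccB, ccA or equivocal. The classifier first assigns a mixed core to its closest match. Each result is then reviewed, and "samples that show clear elements of both types in expression patterns will be labeled as equivocal". The quantity carried forward is narrow: "The fraction of samples classified as clearly ccB will be used in further analysis". The denominator is given only as samples; nothing says whether equivocal cores, or cores without a result, stay in it.

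The aim is worded in two ways.

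- **Broader wording.** Section 2.1.1 correlates the imaging metric "with the fraction of ccB-positive cores based on transcript analysis". The purpose sentence of section 7.1 speaks of PET-MR "in predicting the fraction of tumor cores expressing the ccB subtype". Section 1.1 says: "The primary objective is to evaluate the capabilities of MRI/PET in prediction of ccB burden".
- **Narrower wording.** The hypothesis (sections 1.1 and 1.3), the primary-endpoint sentence of section 7.1 and section 7.3 (where FTVOT2 is correlated with "the primary outcome (fraction of core classified as ccB") all refer to cores classified as ccB.

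Section 7.3 uses Spearman's correlation with N = 17 and states power of 54% at rho 0.5 and 74% at rho 0.6. It cites a prior-study Spearman correlation of .896 between FTVOT2 and the fraction of cores classified as ccB.

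**The concern.** By the plan's own definition an equivocal core contains ccB. If all cores form the denominator, it nevertheless scores the same as a pure ccA core. Section 1.2 reports that "many of the upregulated genes associated with ccB were involved in glucose transport and metabolism, the mediators of 18-FDG uptake". On that reasoning mixed tissue might raise FTVOT2 while adding nothing to the outcome it is compared with.

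Spearman's test uses only the ordering of 17 tumours, so ties and misordering matter. A tumour with 3 ccB and 7 equivocal cores would rank below one with 4 ccB and 6 ccA cores, and ten equivocal cores would tie with ten ccA cores. If this weakens the correlation, a study with little power loses some of it. The estimate may also be used later, since section 1.1 says: "Information from this study may be used to estimate effect size for power calculation".

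**Working it through.** **1. The plan's power figures.** Inputs from section 7.3: N = 17, alpha 0.05 (taken as two-sided). By Fisher's z, power = Φ(atanh(ρ)·√(N − 3) − 1.96).

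- ρ = 0.5: Φ(0.549 × 3.742 − 1.96) = Φ(0.095) = 53.8%
- ρ = 0.6: Φ(0.693 × 3.742 − 1.96) = Φ(0.634) = 73.7%

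Both stated figures reproduce. They take rho as the correlation with the outcome as scored, so the treatment of equivocal cores does not alter them.

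**2. What the scoring rule does to ten-core tumours.** Written = ccB/10; half = (ccB + 0.5 × equivocal)/10; any = (ccB + equivocal)/10; excluded = ccB/(ccB + ccA).

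| Tumour | Written | Half | Any | Excluded |
|---|---|---|---|---|
| 3 ccB, 7 equivocal | 0.30 | 0.65 | 1.00 | 1.00 |
| 4 ccB, 6 ccA | 0.40 | 0.40 | 0.40 | 0.40 |
| 10 equivocal | 0 | 0.50 | 1.00 | undefined |
| 10 ccA | 0 | 0 | 0 | 0 |

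The rule can change ranks. If ccB-positive is read literally, though, the implied weight for an equivocal core is 1. No section supports 0.5.

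**3. Power if mixed cores lie midway between the types.** All inputs here are assumptions except N and the ten-core maximum: tumour ccB content p ~ Beta(0.7, 1); core content ~ Beta(cp, c(1 − p)); a core is equivocal if its content lies between w and 1 − w; Spearman correlation 0.6 between FTVOT2 and p; 10,000 replicates. The equivocal share comes out at 9–32%.

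| c / w | Written | Half | Gain (points) |
|---|---|---|---|
| 0.7 / 0.25 | 62.4% | 65.8% | 3.4 |
| 0.7 / 0.35 | 63.4% | 65.0% | 1.6 |
| 1.5 / 0.25 | 61.5% | 67.1% | 5.6 |
| 1.5 / 0.35 | 62.8% | 66.0% | 3.2 |
| 3 / 0.25 | 60.5% | 68.6% | 8.1 |
| 3 / 0.35 | 62.8% | 67.6% | 4.8 |

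Mean sample rho is 0.51–0.53 as written and 0.54–0.55 with half credit. Under the null both reject in 5.0–5.4% of trials. The equivocal band is symmetric about 0.5, so this model makes half credit close to correct by construction.

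**4. Power if mixed tissue is a component of its own.** Tumour shares of ccA, equivocal and ccB are Dirichlet (0.7, e, 0.5) with e = 0.1, 0.25 or 0.55. The mean equivocal share is e/(1.2 + e): 0.1/1.3 = 8%, 0.25/1.45 = 17%, 0.55/1.75 = 31%. FTVOT2 tracks ccB + k × equivocal, again at Spearman 0.6. Entries are power with half credit minus power as written, in points.

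| k | 8% equivocal | 17% | 31% |
|---|---|---|---|
| 0 | −6 | −12 | −19 |
| 0.05 | −3 | −7 | −10 |
| 0.10 | −1 | −4 | −5 |
| 0.15 | −0.5 | −1 | −2 |
| 0.25 | +1 | +4 | +5 |
| 0.50 | +5 | +12 | +19 |
| 1 | +13 | +25 | +34 |

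Repeat runs move entries by a point or two; at k = 0.10, for example, a repeat gave losses of 2 to 7 points. The sign changes at a k of roughly 0.15 to 0.2. Half credit therefore loses over a range of k, not only when mixed tissue behaves exactly like ccA.

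**The case for a change.** The best case for changing the outcome has three parts.

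- **A weight of 0 is as arbitrary as 0.5, and more extreme.** For a core with clear elements of both types, the midpoint is the neutral choice.
- **The biology favours some uptake.** The rationale in section 1.2 makes a mixed-tissue effect near zero less likely, and at a quarter of the ccB effect the graded score is already slightly ahead. In the midway model the rule as written scores 22–46% of tumours 0, and about one third to two thirds of those hold at least one core with clear ccB elements. Where ccB is rare the gain can be large: in one such setting (32% equivocal, mean ccB burden 0.2) power was 20% as written and 64% with half credit.
- **The cost looks small.** No new tissue, assay or patients are needed, and the two outcomes coincide if no core is equivocal.

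The mismatch with the broader wording stands, as does the possibility of a gain. The claim that the graded score is the better primary outcome does not. Section 1.2 concerns genes associated with ccB; uptake in mixed tissue is an inference from it. The cost also exceeds one sentence. The primary outcome would move off the scale of the prior-study correlation of .896, in a study already at Amendment 4 with patients evaluated, and section 8.6 requires IRB approval before an amendment is implemented. Finally, attenuation does not mislead a later study that keeps the same outcome, because the estimated rho is then the correct planning input.

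**Conclusion.** No change to the plan follows. Section 7.1 states an outcome rule that fits the hypothesis, the primary endpoint and section 7.3: with three labels available, a core labelled equivocal has not been classified as ccB. The looser phrases in sections 2.1.1 and 1.1 and in the purpose sentence of 7.1 describe the aim and do not define the measurement.

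Replacing the outcome with a half-credit score is a trade-off of unknown sign. Across the assumptions tried, the change in power ran from a loss of 19 points to a gain of 44, and it was a gain of 2 to 8 in the main setting, which favours half credit by construction. The result turns on the equivocal rate and on FDG uptake in mixed tissue. The documents give neither, so every simulated figure here is conditional. Type I error is about 5% either way, and the stated 54% and 74% are unaffected.

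What remains is missing detail: one phrase for the outcome, the denominator, and a count of equivocal cores per tumour. Scoring equivocal cores as zero is itself only the literal reading, because the denominator is not defined. An analyst would ordinarily divide by the ccRCC cores that yield a classifier result, tabulate the equivocal ones and look at other scorings alongside the main result. In a 17-patient study meant to give preliminary information, that is adequate.
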